3 GENERAL ANALYSIS CONVENTIONS

The safety analyses will be performed using the safety population. In general, safety analyses will be presented by gene mutation (e.g., BRCA1/2, ATM, CDK12, CHEK2, and Other) and Overall. Safety data may also be presented by subgroups (e.g., measurable disease status at baseline or germline/somatic status for BRCA patients).

In general, efficacy analyses will be presented by gene mutation based on study entry test results (e.g., BRCA1/2, ATM, CDK12, CHEK2, and Other) and Overall. The CRF has several questions regarding gene mutations. The first asks “Does the patient have a deleterious mutation of either BRCA1, BRCA2 or ATM?” and only 1 can be selected. A second question asks “Does the patient have a deleterious mutation of another gene associated with HRD?” and 12 other gene mutations are listed, and more than 1 can be selected. Patients will be categorized into 1 of several gene mutation groups defined as follows:

- BRCA: if BRCA1 or BRCA2 is selected in the first question (regardless of any others being selected in the second question)

- ATM: if ATM is selected in the first question (regardless of any others being selected in the second question)
- CDK12: if the answer to the first question is “No” and only CDK12 is selected in the second question
- CHEK2: if the answer to the first question is “No” and only CHEK2 is selected in the second question
- Other: all others.

Note: Other gene mutation groups may be added depending on the number of patients with a specific gene mutation.

As mentioned in [Section 2.2](#), patients are enrolled in 1 of 3 cohorts based on measurable disease status at baseline per investigator and based on gene mutation. However, patients could be classified in a different cohort based on IRR assessment of measurable disease at baseline. For example, a patient with a deleterious BRCA1/2 mutation who is assessed to have measurable disease by the investigator would be categorized into Cohort A for analysis of endpoints dependent upon measurable disease status per investigator. However, if this patient was determined to not have measurable disease per IRR, he would not be categorized into Cohort A for analysis of endpoints dependent upon measurable disease status per IRR. As a convention in this SAP, cohort labels (i.e., Cohort A, Cohort B, and Cohort C) will refer to the group of patients associated with the specified analysis (i.e., per investigator or per IRR).

Quantitative variables will typically be summarized using frequencies and percentages for appropriate categorizations and may also be summarized using descriptive statistics. For variables summarized with descriptive statistics, the following will be presented: N, mean, standard deviation, median, minimum, and maximum. Categorical variables will be presented using frequencies and percentages.

The Kaplan-Meier methodology will be used to summarize time-to-event endpoints. If estimable, the 50th percentile (median) with the 95% confidence interval and range (minimum, maximum) will be summarized. The number of patients with events and the number of censored patients will also be presented.

All data will be used to their maximum possible extent but without any imputations for missing data. Unless otherwise specified, baseline is defined as the last measurement on or prior to the first day of study drug administration.

4 ANALYSIS POPULATIONS

The following analysis populations are defined for the study:

Safety Population – The safety population will consist of all patients who received at least 1 dose of protocol-specified treatment.

IRR Efficacy Population – The IRR efficacy population will be defined by measurable disease status at baseline using modified RECIST Version 1.1 criteria per independent radiology review.

- For endpoints using radiographic data, all treated patients with measurable disease (per IRR) at baseline will be included.
- For PSA endpoints, all treated patients without measurable disease (per IRR) at baseline and with a baseline PSA value $\geq 2\text{ng/ml}$ will be included.

Investigator Efficacy Population – The Investigator efficacy population will be defined by measurable disease status at baseline using modified RECIST Version 1.1 criteria per the investigator (Inv).

- For endpoints using radiographic data, all treated patients with measurable disease (per Inv) at baseline will be included.
- For PSA endpoints, all treated patients without measurable disease (per Inv) at baseline and with a baseline PSA value $\geq 2\text{ng/ml}$ will be included.

5 PATIENT DISPOSITION

Patient disposition will be summarized using frequency counts and the corresponding percentages. The number of patients in each analysis population, number of patients discontinued, and the primary reason for discontinuation will be summarized.

A protocol deviation review process/committee will determine the importance of various protocol deviations. The number of patients with important protocol deviations (e.g., those considered to potentially impact the integrity of the analysis or thought to be relevant) will be determined prior to data base lock and will be summarized with frequencies and percentages or provided in a patient listing. Patients will not be excluded from efficacy or safety analyses due to protocol violations.

6 DEMOGRAPHICS AND BASELINE CHARACTERISTICS

All demographic and baseline characteristics will be summarized for the safety population.

6.1 Demographics

The demographic variables will be summarized with frequency tabulations and descriptive statistics. The demographic variables presented will include the following categorizations:

- Age (years): <65 , $65-74$, ≥ 75 and separately ≤ 50 , $51-60$, $61-70$, $71-80$, $81-90$, > 90 ;
- Height (cm): ≤ 75 , $> 75-100$, $> 100-125$, $> 125-150$, $> 150-175$, > 175 ;
- Weight (kg): ≤ 50 , $> 50-75$, $> 75-100$, $> 100-125$, $> 125-150$, > 150 ;

- Race: American Indian or Alaska Native, Asian, Black, Native Hawaiian or Pacific Islander, White, Other, Not Reported;
- Ethnicity: Hispanic or Latino, Not Hispanic or Latino, Not Reported, Unknown;
- Smoking status: Current Smoker, Former Smoker, Never Smoked;
- Region: North America, Europe, and Other

6.2 Baseline Clinical Characteristics

Baseline characteristics, including the following variables, will be summarized with frequency tabulations:

- Time since diagnosis of primary tumor (years): 0-3, >3-6, >6-9, >9;
- ECOG Performance Status: 0, 1, ≥ 2 ;
- Gleason score (< 7, 7, 8, 9, 10, not reported);
- HRR gene mutation;
- Germline status for patients with a BRCA mutation (Germline, Somatic, Unknown);
- Measurable disease status;
- Type of measurable disease (nodal only, visceral +/- nodal);
- Prior anticancer therapies for prostate cancer;
- Number of prior anticancer therapies for CRPC.

Descriptive statistics may also be used to summarize the continuous variables.

6.3 Medical History

Medical history events will be classified using the Medical Dictionary for Regulatory Activities (MedDRA) classification system version 20.1 or higher. Medical history data will be summarized using frequency tabulations by system organ class and preferred term.

7 PRIOR AND CONCOMITANT MEDICATIONS

All concomitant treatments documented during the study period will be summarized in frequency tabulations. Prior/concomitant medication coding will utilize World Health Organization (WHO) Drug version 2017MAR (Enhanced) or higher.

Separate data summaries of prior medications will be provided. Prior medications will be defined as those medications with both a start and a stop date that is before the day of the first dose of study drug administration. If either the start date and/or the stop date of the medication is missing so that it is unclear whether the medication was stopped prior to first dose of study drug administration, then the medication will be included in the summary of the concomitant medications.

8 STUDY DRUG EXPOSURE AND COMPLIANCE

Duration of treatment will be calculated as 1+ the number of days from study drug start date to date of discontinuation. Descriptive statistics and frequencies/percentages for appropriate categorizations will be used to summarize treatment duration.

9 EFFICACY VARIABLES

9.1 Primary Efficacy Variables

For Cohort A, the primary efficacy endpoint for the study is confirmed radiographic ORR (CR or PR per modified RECIST Version 1.1 criteria and no confirmed bone progression per PCWG3 prior to a CR or PR) by central IRR in patients with measurable visceral and/or nodal disease at baseline per IRR.

For Cohort B, the primary efficacy endpoint is confirmed PSA response ($\geq 50\%$ decrease) as assessed by a local laboratory in patients without measurable disease at baseline per IRR.

For Cohort C, the primary endpoint is confirmed radiographic ORR if measurable visceral and/or nodal disease (per IRR) is present at baseline or confirmed PSA response ($\geq 50\%$ decrease) if measurable visceral and nodal disease (per IRR) is absent at baseline.

Supportive analyses will also be conducted using measurable disease status at baseline per the Investigator.

9.2 Secondary Efficacy Variables

Secondary variables include:

- Duration of response (DOR) (modified RECIST 1.1 or PSA $\geq 50\%$, separately)
- Radiographic progression-free survival (rPFS)
- Overall survival (OS)
- Clinical benefit rate (CBR)
- PSA response $\geq 50\%$ (all patients)
- PSA response $\geq 90\%$ (all patients)
- Time to PSA progression
- AEs, clinical lab abnormalities, and dose modifications
- Trough (C_{\min}) level plasma rucaparib concentrations

9.3 Exploratory Efficacy Variables

Exploratory variables include:

- Patient reported outcomes (PROs) including
 - EQ-5D-5L instrument and the EQ VAS

- FACT-P
- BPI-SF
- Analgesic drug score
- Plasma and tissue genomic profiling results
- ORR and/or PSA response in relation to germline/somatic status (patients with a BRCA1/2 alteration)
- Time to first subsequent antineoplastic therapy
- Percentage genomic loss of heterozygosity (%LOH)
- Best change from baseline in PSA at any time

10 EFFICACY ANALYSIS

In general, efficacy analyses will be presented by gene mutation (e.g., BRCA1/2, ATM, CDK12, CHEK2, and Other) and Overall.

Efficacy analyses for the endpoints using radiographic data for the Cohort A sub-cohorts (i.e., BRCA1/2 and ATM) will be conducted using the IRR Efficacy Population (patients evaluable for response by modified RECIST/PCWG3 criteria per IRR). Supportive analyses will also be conducted using the Investigator Efficacy Population.

PSA-related efficacy analyses for Cohort B (patients without measurable disease at Baseline) will be conducted using patients evaluable for PSA response.

Cohort C will consist of some patients with measurable disease at Baseline and some patients without measurable disease at Baseline. Efficacy analyses for Cohort C will be conducted similarly to Cohorts A and B, dependent upon measurable disease status. Generally, Cohort C will be divided up by gene mutation (e.g., CDK12, CHEK2, and Other), when warranted by the numbers of patients with a specific mutation. These categories will typically appear on the outputs in columns along with the BRCA and ATM columns.

Some efficacy endpoints can be assessed regardless of measurable disease status (e.g., PSA response, CBR, rPFS). These endpoints may also be summarized for all patients, regardless of measurable disease status at Baseline. Additionally, the primary efficacy endpoint will also be presented by age group (< 65, 65-74, ≥ 75) and race (White, Other).

10.1 Primary Efficacy Analysis

For Cohort A, the primary efficacy endpoint is confirmed radiographic ORR by central IRR (as described in [Section 9.1](#)) in patients with measurable visceral and/or nodal disease at baseline. To be considered a responder at a specific time point, a patient must have a CR or PR assessment per modified RECIST and no confirmed bone progression per PCWG3 on or prior to a CR or PR. To be considered a confirmed responder, a patient must have at least 2 responses at least 4 weeks apart prior to a modified RECIST/PCWG3 progression event.

Confirmed radiographic ORR will be summarized with frequencies and percentages along with 95% confidence intervals. The frequency and percentages of patients with a best overall response of complete response (CR), partial response (PR), stable disease (SD), or progressive disease (PD) will also be summarized.

An analysis of confirmed radiographic ORR by the investigator will also be conducted as supportive to the primary endpoint and will use the Investigator Efficacy Population (patients evaluable for response by modified RECIST/PCWG3 criteria per investigator).

For Cohort B, the primary efficacy endpoint is confirmed PSA response as assessed by a local laboratory in patients without measurable disease at baseline (by central IRR). Confirmed PSA response is defined as having 2 consecutive PSA values (at least 3 weeks apart) that are at least 50% lower than baseline and that occur prior to PSA progression (as defined in [Section 10.2.6](#)). Per PCWG3, early rises (before 12 weeks following first dose of study drug) in PSA should be ignored when determining PSA response. Confirmed PSA response will be calculated for patients with PSA values at baseline.

Confirmed PSA response will be summarized separately, with frequencies and percentages along with 95% confidence intervals, for patients without measurable disease per IRR (primary endpoint) and without measurable disease per Investigator (supportive analysis). PSA response will also be summarized for patients with measurable disease (both IRR and Investigator, separately) and for all patients.

For Cohort C, the primary endpoint is confirmed radiographic ORR (by central IRR) if measurable visceral and/or nodal disease is present at baseline [as described for Cohort A] or confirmed PSA response ($\geq 50\%$ decrease from baseline) if visceral and nodal disease is absent at baseline [as described for Cohort B]. This endpoint will be summarized with frequencies and percentages along with 95% confidence intervals.

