9 STUDY PROCEDURES AND ACTIVITIES BY VISIT

9.1 Schedule of Assessments

[Table 5](#) summarizes the procedures and assessments to be performed for all patients. Study procedures and assessments should be performed as close to the scheduled time as possible, but within ± 3 days of the scheduled time unless otherwise stated.

Table 5. Schedule of Assessments

Procedure ^a	Pre-screening Phase	Screening Phase		Treatment Phase					Post-Treatment Phase		
				Week 1	Week 3	Week 5	Week 7	Week 9 & every 4 weeks thereafter			
		Day -28 to Day -1	Day -14 to Day -1	Study Day 1 ^b	Study Day 15	Study Day 29	Study Day 43	Day 57 & every 28 days thereafter	Treatment Discontinuation	28-day Follow-up	Long-term Follow-up
Informed Consent	X ^c	X									
BRCA, ATM or other HRR gene mutation assessment from ctDNA blood and tumor sample ^{c, d}	X ^c										
Medical/Oncology History ^e		X									
Blood samples for plasma ctDNA analysis ^f		X		X		X		X	X		
Physical Examination, Weight, Height ^g		X		X	X	X	X	X	X	X	
Vital Signs ^h		X		X	X	X	X	X	X	X	
12-lead ECG ⁱ		X							X		
Prior/Concomitant Medications/Procedures		X		X	X	X	X	X	X	X	
Tumor Assessment/CT/MRI and Bone Scan ^j		X		End of every 8 weeks from Study Day 1, up to 24 weeks (Study Weeks 9, 17, 25) and then every 12 weeks thereafter (Study weeks 37, 49, 61, etc.) ^k					X ^l	X ^l	X ^l
Archival Primary/ Metastatic Tumor Tissue Sample for retrospective testing ^m		X									
Patient-reported outcome (BPI-SF, analgesic drug score, FACT-P, EQ-5D-5L) ⁿ			X	X		X		X	X	X	X
ECOG Performance Status			X	X	X	X	X	X	X	X	
Serum Testosterone		X									
PSA Measurement ^o		X		X		X		X	X		
Clinical Laboratory Assessments ^p			X	X	X	X	X	X	X	X	
Pharmacogenomic blood sample ^q				X							
Study Drug Dispensation				X		X		X			
Adverse Events ^r	(X)	(X)	(X)	X	X	X	X	X	X ^s	X ^s	
Plasma PK Sample						X ^t		X ^t			

Post-progression Tumor Biopsy (Optional)										X ^u		
Subsequent Treatments, AESIs, & Survival ^v											X	X

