- ^k = Disease assessment by CT/MRI and bone scans will be performed during screening, during the treatment phase, and Treatment Discontinuation, and if applicable, during follow up. Modified RECIST 1.1/PCWG3 criteria will be used. If a CR or PR is noted, confirmatory scans should be performed at least 4 weeks after the initial response was first documented.

- ^l = Radiologic assessments should continue for all patients until confirmation of radiographic progression per investigator assessment, including any patient who discontinued from study treatment for reason other than disease progression or death. Tumor assessments should be performed during the Treatment Discontinuation visit, 28-day Follow-up, or during Long-term Follow-up if the reason was other than radiologically confirmed disease progression and it has been ≥ 8 weeks (≥ 12 weeks if previous scan was after 24 weeks on study) since the last assessment. Tumor assessments should continue on schedule (ie, every 8 or 12 weeks) during Long-term Follow-up until radiographically confirmed disease progression.
- ^m = If archival primary or metastatic tumor tissue was not submitted during Pre-Screening, a specimen should be submitted during the Screening period or after enrollment for retrospective testing by the central laboratory. Archival tissue submitted during Screening for retrospective testing can be > 3 years old. Refer to the Pathology Charter for detailed sample handling instructions.
- ⁿ = The BPI-SF, analgesic drug score, FACT-P, and EQ-5D-5L instruments should be completed prior to other scheduled study procedures and dosing (if applicable). During long term follow up, if possible, PROs to be collected to coincide on days when tumor assessments are performed.
- ^o = All PSA measurements are performed by the local laboratory. Serial PSA measurements that show progression at study entry must follow the protocol specification.

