9.5.5 Study Day 57 (Week 9) and Every 28 Days Thereafter

Patients will be instructed to refrain from taking their first dose of rucaparib at home on study visits when plasma samples are collected for PK.

Plasma samples for PK analysis should be collected before the morning dose on Study Day 57, Day 85, and Day 113 as close to 12 hours after the previous dose as possible. If the start of the next dose is delayed, the PK sample should still be collected during this visit instead of the delayed start of the next study visit;

The following procedures will be completed:

- PRO collected using the BPI-SF ([Appendix 6](#)), FACT-P ([Appendix 7](#)), EQ-5D-5L ([Appendix 8](#)), and analgesic drug score instruments ([Appendix 9](#); should be completed before other procedures)
- Physical examination
- Weight
- Vital signs
- Tumor assessment scans at the end of every 8 calendar weeks (± 7 days) for the first 24 weeks (Weeks 9, 17, 25), and then every 12 calendar weeks (± 7 days) thereafter (Weeks 37, 49, 61, etc)
- Concomitant medications and procedures
- ECOG performance status ([Appendix 3](#))
- PSA measurement
- Hematology

- Serum chemistry (fasting is not required)
- Urinalysis
- Plasma sample for ctDNA
- Plasma sample for PK analyses (Study Day 57, Day 85, and Day 113 only)
- AE (inclusive of SAE and AESI) monitoring
- Dispensation of rucaparib

Patients will ingest rucaparib twice daily at about the same times every day as close to 12 hours apart as possible. Rucaparib should be taken with at least 8 oz (240 mL) of water with or without food. Patients will keep all unused containers (empty, partially used, and/or unopened) and return with them to the study site for accountability at the next visit. In the event of toxicities, re-treatment or dose modification will be according to the criteria described in [Section 7.4.2](#).

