11.5.2 Secondary Efficacy Analysis

Duration of confirmed response is defined as the time from the date that a response (modified RECIST 1.1 or PSA $\geq 50\%$) is first reported to the time that progression is first documented:

- For responses per RECIST 1.1, duration of confirmed response is defined as the time from the date that a response (modified RECIST 1.1) is first reported to the time that progression (per modified RECIST Version 1.1 criteria or bone progression per PCWG3) is first documented
- For PSA-response, duration of confirmed response is defined as the time from the date that a response (PSA decrease $\geq 50\%$) is first reported to the time that PSA progression is first documented

Radiologic PFS (rPFS) is defined as the time from first dose of rucaparib to the date of first objective evidence of radiographic progression (soft tissue or bone lesion) or death due to any cause, whichever occurs first. Radiographic disease progression includes confirmed bone disease progression and soft tissue disease progression adjudicated by independent central radiological review using the PCWG3 guidelines for bone disease and modified RECIST Version 1.1 for soft tissue disease.

OS is defined as the date from first dose of rucaparib to the date of death due to any cause.

Clinical benefit rate (CBR) is defined as the combination of CR, PR, and SD as defined by modified RECIST Version 1.1 and no progression in bone by PCWG3 criteria. Per RECIST, to be assigned a best overall response of CR or PR, changes in tumor measurements must be confirmed by repeat assessments that should be performed no less than 4 weeks after the criteria for response are first met.

Confirmed PSA response is defined as $\geq 50\%$ reduction in PSA from baseline to lowest post-baseline PSA result, with a consecutive assessment conducted at least 3 weeks later. PSA response will be calculated for all patients with PSA values at baseline and at least 1 post-baseline assessment. PSA will be assessed by a local laboratory.

Similarly, PSA response will also be define as $\geq 90\%$ reduction in PSA from baseline to lowest post-baseline PSA result, with a consecutive assessment conducted at least 3 weeks later.

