10.2.6 Time to PSA progression

Time to PSA progression is defined as the time from first dose of rucaparib to the date that a $\geq 25\%$ increase and absolute increase of ≥ 2 ng/mL above the nadir (or baseline if there was no PSA decline after baseline) in PSA was measured, plus 1 day. The increase must be confirmed by a second consecutive assessment conducted at least 3 weeks later (unless the PSA progression occurred at the last recorded PSA assessment). If confirmed, the date used for time of PSA progression is the earlier of the 2 PSA dates. Additionally, early rises (before 12 weeks following first dose of study drug) are not considered in determining PSA progression.

Time to PSA progression will be summarized for all patients and may also be summarized for the subgroups of patients defined by measurable disease status at baseline.

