11 STATISTICAL / ANALYTICAL ISSUES

11.1 Handling of Dropouts or Missing Data

All data will be used to their maximum possible extent but without any imputations for missing data. All time to event analyses include censoring and the rules for deriving the censoring value are described in more detail under each one of the time to event endpoints.

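### Read literally, the confirmed PSA response rule can drop a response that rests on exactly two scheduled values when an extra PSA falls midway between them, and the parallel progression rule can date progression one visit late

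*SAP*

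**What the plan says.** SAP 10.1 defines the Cohort B primary endpoint, which also serves Cohort C patients without measurable disease: "Confirmed PSA response is defined as having 2 consecutive PSA values (at least 3 weeks apart) that are at least 50% lower than baseline". The pair must come before PSA progression, and early rises in the first 12 weeks are ignored. SAP Table 1 and Section 13 repeat the rule, and 10.2.5 extends it to all patients and to the 90% threshold. Protocol 11.5.2 has the same element: "with a consecutive assessment conducted at least 3 weeks later".

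For progression, SAP 10.2.6 says: "The increase must be confirmed by a second consecutive assessment conducted at least 3 weeks later". This is waived if the progression is at the last recorded PSA. The event takes the earlier of the two dates, and early rises are not considered.

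On treatment, PSA is listed for Day 29 and then for "Study Day 57 (Week 9) and Every 28 Days Thereafter" (Protocol 9.5.3 and 9.5.5). Procedures fall "within ± 3 days of the scheduled time unless otherwise stated" (Protocol 9.1). No PSA is listed for Day 15 or Day 43. A Table 5 footnote adds: "All PSA measurements are performed by the local laboratory".

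No rule includes or excludes unscheduled values by name. The general convention in SAP 11.1, also in Section 3, is: "All data will be used to their maximum possible extent but without any imputations for missing data".

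For Cohort A, SAP 10.1 does not ask for adjacency: "a patient must have at least 2 responses at least 4 weeks apart prior to a modified RECIST/PCWG3 progression event".

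**The concern.** Adjacency and a minimum gap fit together only while the record holds scheduled values alone. Once another PSA is recorded between two visits, the values that were adjacent no longer are, and the new neighbours may be too close together. A value that agrees with the response can then erase it, which cannot be the intention.

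The Cohort B decision rules are counts (16 of 54 for BRCA1/2, 11 of 33 for ATM), so at the boundary one patient decides the result. Two programmers who read *consecutive* differently could report different counts. For progression the date itself is the outcome. It feeds time to PSA progression, PSA duration of response (10.2.1) and the rPFS sensitivity analysis that uses PSA progression (10.2.2).

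**Working it through.** **1. The plan's own figures.** For Cohort B the exact two-stage rejection probability is

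P(reject | p) = Σ over x from r1+1 to n1 of C(n1,x) p^x (1−p)^(n1−x) × P[Bin(n−n1, p) ≥ R − x],

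where R is the number of responses needed to reject. Inputs are from SAP 2.3.

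- BRCA1/2: n1 = 19, r1 = 4, n = 54, R = 16. Type I error is 0.0482 at p = 0.20; power is 0.9045 at p = 0.40.
- ATM: n1 = 18, r1 = 4, n = 33, R = 11. Type I error is 0.0458; power is 0.8011.

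Both agree with the stated 5% ceiling and the stated 90% and 80% power. The design figures are sound; only the endpoint definition is at issue.

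**2. Scheduled values alone.** Visits 28 days apart, each ±3 days, give gaps from 28 − 6 = 22 to 28 + 6 = 34 days. Every adjacent scheduled pair meets the 21-day minimum.

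**3. Exactly two scheduled qualifying values, one extra.** Let the gap be g and the extra qualifying PSA fall x days after the first value. The pair is broken only if x ≤ 20 and g − x ≤ 20.

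| Gap g | Values of x that break the pair | Days affected |
|---|---|---|
| 22 | 2 to 20 | 19 of 21 |
| 28 | 8 to 20 | 13 of 27 |
| 34 | 14 to 20 | 7 of 33 |

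Example: 60% below baseline on Days 29, 43 (unscheduled) and 57, then 40% below on Day 85. The adjacent gaps are 14, 14 and 28 days. The only pair far enough apart includes the non-qualifying Day 85 value, so this is a non-response. Without Day 43, Days 29 and 57 confirm a response.

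**4. Three or more consecutive scheduled qualifying values, one extra.** The rule needs any one adjacent qualifying pair. With k values there are k − 1 intervals, and one extra PSA can spoil only one of them. Enumerating every possible day at 28-day gaps, confirmation was lost on 0 of 54 days for k = 3 and 0 of 81 for k = 4. For k = 3 with visit shifts of −3, 0 or +3 days it was lost in 0 of 1,458 cases. An extra PSA is needed in every interval to remove the response.

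**5. Progression.** Suppose the criterion is met on Days 85, 99 (unscheduled), 113 and 141. Day 85 is 84 days after first dose, so it is not an early rise. Read literally, 85→99 and 99→113 are 14 days each and do not confirm; 113→141 is 28 days and does. Progression is dated Day 113. Without Day 99, 85→113 confirms and the date is Day 85. The difference is 113 − 85 = 28 days. Later agreeing values confirm the event but do not restore its date.

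**6. Size per affected patient.** 1/54 = 1.9 points and 1/33 = 3.0 points; at the maximum enrolment, 1/100 = 1.0 and 1/50 = 2.0.

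**7. Illustration under assumed loss.** The documents give no frequency of unscheduled PSAs. If a share f of true responders were lost, the response probability would be 0.40 × (1 − f):

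| Assumed f | p | Power, BRCA1/2 | Power, ATM |
|---|---|---|---|
| 0% | 0.400 | 0.9045 | 0.8011 |
| 2% | 0.392 | 0.8877 | 0.7753 |
| 5% | 0.380 | 0.8578 | 0.7327 |
| 10% | 0.360 | 0.7940 | 0.6526 |

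This applies the loss at both stages. The Stage 1 rule is worded as PSA response without confirmation; if it is run that way, the loss of power is no larger than shown.

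**The case against.** A reader might infer that any extra PSA turns a sustained responder into a non-responder, or that closer monitoring generally lowers the response rate. The documents do not support either. One adjacent pair suffices, so a patient whose decline holds over three successive scheduled values keeps the response after one extra PSA. Even with only two values 28 days apart, 14 of the 27 possible days for the extra PSA do no harm.

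The trigger is also not shown to be common. Blood is drawn on Days 15 and 43, but for hematology and chemistry. The permission for more frequent testing in Protocol 9.10.2 covers those panels, not PSA. The PSA at treatment discontinuation is the last one listed, so it does not split two scheduled on-treatment values. The sentence on using all data sits in the missing-data section and says nothing specific about unscheduled values. All of this limits the expected frequency. It does not remove the gap, because nothing excludes such a value once a local laboratory reports it.

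For progression, the wording can also be read as the next assessment at or beyond 3 weeks, which would give Day 85 in the example. That reading is reasonable, but it is not the only one, so the date depends on the programmer. The last-assessment waiver does not help: if Day 113 were the last PSA, the waiver would date progression Day 113 as well.

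**Conclusion.** The point holds in a narrow form and is minor. On the literal text, with unscheduled values included, a response resting on exactly two scheduled qualifying values is lost when a qualifying extra PSA leaves both gaps under 21 days. A mid-interval PSA can also date progression one visit late, which lengthens time to PSA progression and PSA duration of response.

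The response error runs one way. For a given progression date, any adjacent pair that satisfies the literal rule also satisfies the rule proposed below, so the literal rule can only count fewer responders. It cannot inflate the single-arm response rate. As worded, the Stage 1 boundaries do not require confirmation and so do not depend on it. The total effect cannot be estimated from the documents; the power figures above rest on assumed loss rates and are not a forecast.

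**What to change.** In SAP 10.1, define confirmed PSA response as two PSA values at least 3 weeks apart, both at least 50% below baseline and both before PSA progression, with every value between them also meeting the threshold, except early rises before 12 weeks that 10.1 already ignores. Use the same form with 90% in 10.2.5.

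In 10.2.6, confirm progression by a value at least 3 weeks later that still meets the criterion, with no value in between failing it. Date it at the first rise, and state that the last-assessment and early-rise provisions stay. Carry the wording into Table 1 and Section 13.

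Under this text the example patient is a responder on Days 29 and 57, the example progression is dated Day 85, and an extra qualifying PSA can never remove a response. The cost is SAP wording and a small programming change. Sample size (54 and 33), decision rules, visits and data collection are unchanged.
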